The sole recruitment source for this study will be the VA Aspire Center, a 40-bed Residential Rehabilitation Treatment Program serving homeless O/O/O Veterans with mental health conditions such as PTSD, depression, and TBI. A rate of accrual of 10 participants enrolled per quarter during the recruitment period (last three quarters of Year 1; Year 2; first quarter of Year 3) would be required to support our targeted accrual. The average length of stay is 3-6 months, meaning that between 80 and 160 participants per year would be eligible for the study. We aim to enroll 30 participants in the last three quarters of Year 1, 40 in Year 2, and 10 in the first quarter of Year 3, making our enrollment goals feasible. Our research team has held several planning meetings with the Aspire Center team and has identified a plan for successful recruitment that maximizes the possibility that participants will be enrolled while being minimally disruptive to Aspire Center operations. To facilitate recruitment, our PI and study staff will be highly visible at the Aspire Center and will coordinate with program intake staff (please see Letter of Support from [name], LCSW, Chief of the Aspire Center). Individuals who meet the inclusion criteria outlined above will then be approached for potential participation in the study and, if interested, will complete the consenting process and the baseline assessment.

Retention

During the trial, assessments will be administered at baseline, 5 weeks, 10 weeks, and 15 weeks, and brief monthly follow-up phone calls will assess housing and employment/education status for one year following program discharge. Participants will be compensated for their time spent in assessments (\$25 per assessment X 4 assessments = \$100 maximum total compensation) as a way to enhance retention. Based on prior studies of Veterans with PTSD and/or TBI, we expect about 20% attrition, for a final sample size of 78 (39 per group). Attrition may be even lower, given that all participants will be residing on-site. Monthly follow-up assessment of housing/employment status will be brief and not burdensome to participants.

Procedure

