as Random Regression Modeling and Hierarchical Linear Modeling) which takes advantage of all existing data points for minimal loss of data, will be used to analyze the data related to our main hypothesis (H1a). Therefore, we will not impute missing data because our analytic method uses all existing data points, including all subjects with missing data or those who were terminated early in the study, without relying on data imputation procedures (Diggle et al., 1994; Laird & Ware, 1982; Hedeker et al., 1991). The mixed effects approach provides more information and, therefore, more power compared to cross-sectional analyses that focus on the analysis of one summary index or more traditional analytic approaches such as a change score, end-point, or repeated measures analysis of variance (ANOVA). We will also use pattern-mixture models to assess if there is bias due to drop out or missing data. As described by Hedeker and Gibbons (1997), these mixed models allow us to assess whether important estimates are dependent on missing data patterns, and provide overall estimates of effects by averaging over the various missing-data patterns. In addition, we will consider the extension of the Pattern-Mixture models as described by Guo et al. (2004), which includes the incorporation of random effects in the pattern mixture model, allowing subject-to-subject heterogeneity. Missing data will be examined to assess randomness. The pattern of missing data will be examined according to the procedure recommended by Little and Rubin (1987), which includes comparing group differences in the primary outcomes of subjects with versus without missing data. SPSS and SAS statistical software will be used to analyze the data. Type I error will be controlled by a Bonferroni adjustment to the alpha per outcome domain for Hypotheses 1a and 1b. Specific plans for testing each hypothesis are below.

H1a: Positive CCT-associated effects on cognition, functional capacity (co-primary outcomes), and disability will emerge over the 15-week study.

Dependent variables: Cognition (global deficit score [GDS] composite; Heaton, et al., 1995), UPSA-B (co-primary outcomes), WHODAS 2.0.

Independent variables: Treatment group (CCT vs education control) and Time (0, 5, 10, 15 weeks).

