Statistical analyses: We will analyze data on all randomized subjects with a baseline assessment and at least one post-baseline evaluation, using mixed effects models, described above. The mixed effects model method provides an estimate of the individual variability around the population trend, the variability of the individual intercepts (baseline values) and slopes (changes across time), and the correlation between them. A fully saturated treatment by time model will be utilized for inference. Covariance structure will be chosen based on Akaike's Information Criterion (AIC). Random group level treatment effects will also be evaluated for importance based on the model AIC. This method allows for any group level effects to be incorporated into the model. Denominator degrees of freedom will be calculated using the Kenward-Roger small sample correction.

Power Analysis: We used procedures described by Hedeker et al. (1999) for Random Regression Models for the proposed study to estimate needed sample size (the RMASS program provided by Hedeker). We estimated that with a final sample size of 78 (target n=98, with a drop-out rate of 20%), the study will have .80 power to yield a statistically significant result for a .72 effect size, accounting for Type I error correction, .5 correlation between time points, and one random effect in the model. We have previously found CCT-associated effect sizes of .72 for prospective memory functioning in Veterans with mild to moderate TBI (74% of whom had PTSD), as well as for the UPSA-B in individuals with severe mental illness. Although we have not previously used the WHODAS 2.0 to assess disability, we have also found CCT-associated effect sizes of .81-1.0 for quality of life in these populations. The trial was therefore powered to detect effect sizes in the .72 range.

H1b: Positive CCT-associated effects on community reintegration outcomes (housing stability, participation in employment/education, healthcare appointment attendance) will be detected at the end of the 1-year follow-up.

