Dependent variables: Proportion of months housed, proportion of months engaged in productive activity (work or school), and proportion of VA healthcare appointments attended during the 1-year follow up period (all three outcomes based on monthly data collected during the 1-year follow-up period). Any missing data on housing and work/school status will be accounted for by using a proportion based on the available data points. Healthcare appointment attendance will be gathered from CPRS data and will not be subject to missing data.

Independent variable: Treatment group (CCT vs education control).

Statistical analyses: ANOVA models comparing the treatment and control group on the three dependent variables above. We have selected ANOVA over alternative models (t-test; Wilcoxon Rank Sum; Poisson regression) due to the type of dependent variables (continuous) and the option to include any covariates that might be imbalanced between the treatment groups.

Power analysis: With 78 subjects (39 subjects per group), we will have .80 power to detect an effect size of .64, a medium-to-large effect size.

capacity, disability, and community reintegration.

Dependent variables: UPSA-B at 15 weeks, WHODAS 2.0 at 15 weeks, proportion of months housed, proportion of months engaged in productive activity (work or school), and proportion of VA healthcare appointments attended during the 1-year follow up period.

Independent variables: Treatment group (CCT vs education control).

Mediators: Cognitive improvement in GDS composite from 0-10 weeks (slope of change across weeks), improvement in CPSA cognitive strategy use from 0-10 weeks (slope of change across weeks).

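### H1a and H1b use plain Bonferroni: Holm over the same families keeps the familywise error and adds about 5 points of power per co-primary, and the stated H1b power omits the adjustment

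*Combined protocol and SAP*

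**What the plan says.** All of this is in Section 9, Analytic Plan and Power Analyses.

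- **Multiplicity rule:** "Type I error will be controlled by a Bonferroni adjustment to the alpha per outcome domain for Hypotheses 1a and 1b". The overall alpha, its sidedness and the number of outcomes in each family are not given. No step-down or gatekeeping procedure appears elsewhere.
- **H1a outcomes:** the global deficit score (GDS) composite and "UPSA-B (co-primary outcomes), WHODAS 2.0", so two co-primaries and a disability measure.
- **H1a power:** "the study will have .80 power to yield a statistically significant result for a .72 effect size, accounting for Type I error correction". The calculation used the RMASS program, with "accounting for Type I error correction, .5 correlation between time points, and one random effect in the model".
- **H1b outcomes:** months housed, months in work or school, and VA healthcare appointments attended, all as proportions. Each is compared between groups by ANOVA.
- **H1b power:** "we will have .80 power to detect an effect size of .64, a medium-to-large effect size", for 39 per group. This statement mentions no correction.
- **Sample size** (also under Retention): "we expect about 20% attrition, for a final sample size of 78 (39 per group").

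**The concern.** Bonferroni tests every outcome in a family at the same reduced level, whatever the other outcomes show. Holm tests the smallest p-value at that level. If it is rejected, Holm tests the next at a less strict level, and so on. Every Bonferroni rejection is therefore also a Holm rejection, and familywise error stays at or below the same bound without any assumption about correlation.

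The trial expects only 39 completers per arm. With plain Bonferroni it could win one co-primary clearly and miss the other at a p-value that Holm would accept, with no stricter bound on familywise error in return.

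The H1b power statement raises a second point. The multiplicity rule covers H1b, yet the quoted .80 looks like an unadjusted figure.

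**Working it through.** **Inputs.** From the documents: 98 × 0.80 = 78.4, so 78 analysed and 39 per group; effect sizes .72 (H1a) and .64 (H1b); two co-primaries plus WHODAS 2.0; three H1b outcomes. Assumed: two-sided familywise .05, one t-type contrast per outcome, and correlation 0 to .5 between outcome statistics. The .5 in the protocol is between time points, not between outcomes.

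**Step 1: the plan's own figures.** The noncentrality is d × √(n/2), with √(39/2) = 4.416. That gives 3.179 for d = .72 and 2.826 for d = .64. Power is the noncentral t tail on 76 df, with the normal approximation in brackets.

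| Two-sided alpha | d = .72 | d = .64 |
|---|---|---|
| .05 | .881 (.889) | .797 (.807) |
| .025 | .812 (.826) | .705 (.721) |
| .0167 | .766 (.784) | .648 (.667) |

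For H1a, .80 is clearly a corrected figure, since unadjusted power would be .88-.89. It is compatible with .025 (.812 by t) and with .0167 (.784 by normal approximation). For H1b, .80 matches only the unadjusted row.

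**Step 2: two co-primaries at .72, zero correlation.** Write a = .812 (power at .025) and b = .881 (power at .05), so b − a = .069.

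- Both significant, Bonferroni: a² = .659.
- Both significant, Holm (both at or below .05, at least one at or below .025): b² − (b − a)² = .776 − .005 = .771.
- Each outcome, Holm: a + (b − a) × a = .812 + .056 = .868.
- At least one, either method: 1 − (1 − a)² = .965.

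At correlation .5, simulated t statistics give about .86 for each outcome under Holm. Both are significant in .70 under Bonferroni and .79-.80 under Holm.

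**Step 3: three H1b outcomes at .64, zero correlation.** Write a = .648, b = .705 and c = .797 for power at .0167, .025 and .05. Holm power for one outcome has three parts:

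- p at or below .0167: .648.
- p between .0167 and .025, with at least one other at or below .0167: .057 × (1 − .352²) = .057 × .876 = .050.
- p between .025 and .05, with both others at or below .025 and at least one at or below .0167: .092 × (.705² − .057²) = .092 × .494 = .045.

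The sum is .743, against .648 under Bonferroni. At correlation .5, simulation gives .73.

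**Step 4: familywise error, two outcomes.** With both nulls true, the methods agree: .049 at correlation 0 and .047 at .5. With one null true and the other outcome powered at .80, Holm gives .045 and .043 against .025 for Bonferroni. All are below .05.

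**Step 5: when the gain is smaller or larger.**

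- Only one co-primary has an effect: gain (b − a) × .025 = .069 × .025 = .0017, about 0.2 points.
- Effects .72 and .50: the weaker goes from .47 to .57.
- Correlation .7 to .9, starting from .80 each: 4.1 to 3.2 points per outcome and 8.2 to 6.5 for both.
- H1a as a family of three at .72 (normal approximation): from .784 to .85-.87 each.

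**The case against.** **Bonferroni is valid.** This stands. The issue is lost efficiency, not an error, and Design Considerations calls this a pilot trial. The gain depends on more than one effect being real.

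**The family is not defined.** This also stands. The adjustment is described by outcome domain, without a count, so the two-outcome H1a figures are one reading. Holm is no less powerful than Bonferroni for any family size, but the plan must name the family.

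**The success rule is open.** If success required both co-primaries, no alpha split would be needed. Each would be tested at .05, with joint power .881² = .776 at zero correlation, and neither method would apply. The documents state no such rule, and adjusting alpha fits separate claims better.

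**A stronger reading of the H1a power.** A reader might infer that .80 holds only for two outcomes at .025, so that true power over three domains is .77. The documents do not support this. The normal approximation at .0167 gives .784, and the RMASS contrast is not stated. If one assumes four visits, compound symmetry at .5 and a linear effect reaching .72, normal-theory power is .87 at .025 and .83 at .0167. An endpoint t test cannot show which alpha was used.

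**A tempting addition.** One might test WHODAS 2.0 only after both co-primaries succeed. That is no longer Holm and can lose power. With WHODAS 2.0 at .72, three-way Bonferroni gives .77. The gate gives .68-.74 if both co-primaries are .72, .45-.53 if one is .50, and only about .03-.04 if one has no effect. Holm over all three gives .80-.86.

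**Conclusion.** The point holds as a cheap improvement in efficiency. Under the stated assumptions, and with every effect in the family real at the planned size:

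- **H1a, two co-primaries at .72:** .81 to .86-.87 each, and .66-.70 to .77-.80 for both.
- **H1b, three outcomes at .64:** .65 to .73-.74 each.

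The chance of at least one success is unchanged. None of this shows that Type I error is uncontrolled or that the H1a figure of .80 is wrong.

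The H1b figure is a separate inconsistency. At .64 with 39 per group, power is .797 at unadjusted .05. It falls to .705 if alpha is halved and .648 if it is split three ways. The quoted .80 therefore does not reflect the adjustment that the same section prescribes for H1b.

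**What to change.** 1. In the Type I error sentence, replace the Bonferroni adjustment with a Holm adjustment at familywise two-sided .05, applied within H1a and within the three H1b outcomes.
2. Name the H1a family explicitly, using the one behind the sponsor's power calculation. If WHODAS 2.0 was counted there, keep it in the Holm family, with no gate on the co-primaries. State whether each co-primary may be claimed separately.
3. Restate the H1b power at .64: about .65 per outcome under three-way Bonferroni or at Holm's first step, and about .73-.74 overall with Holm if all three effects are .64.

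The cost is a few sentences, with no added participants or measurements; the change should be made before any unblinded analysis. The one downside is that Holm-adjusted simultaneous confidence intervals are less simple than Bonferroni ones. Unadjusted intervals can be reported beside Holm-adjusted p-values.

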Following study enrollment, participants will complete a baseline assessment and will then be randomly assigned to receive either CCT or the education control condition, "Holistic Cognitive Education," for 10 weeks, as described in Table 1. All treatment will be provided by the Cognitive Specialist, a doctoral level neuropsychologist with experience in cognitive rehabilitation. Note that one page (page 4) of the CCT manual (Appendix 1) contains education regarding TBI, and we do not expect all participants to have a history of TBI. If a participant does not have a history of TBI, page 4 will be skipped.

The Cognitive Specialist and the participant will choose whether to receive sessions in-person at the clinic or via home-based video telemedicine (HBVT) modality. To assure patient confidentiality and HIPAA compliance, we will use VA-approved software, such as the VA Video Connect platform currently in use within the VA. Final selection of HBVT software will be performed at the time of study launch to avoid issues related to changes in policy, access, or availability. These software packages allow standard computers with standard connections to teleconference (video and audio) in real time, using federal government tested and approved encryption. Importantly, these software encryption packages meet Federal Government Standards for encryption at a level that does not require a virtual private network (VPN; however, the software is VPN compatible) and this encryption is already Federal Information Processing Standard (FIPS) 140-2 certified and can be installed on Federal government and VA computers. Further, the study team has successfully implemented and used this software in two ongoing clinical trials evaluating HBVT service delivery of mental health services to Veterans. The most recent Home-Based Telemental Health Standard Operating Procedures Manual [61] will be used in order to best implement HBVT. Data on the type and amount of assistance required for successful home-based delivery will be tracked.

Randomization will be carried out by the Research Health Scientist, based on randomization tables created by the statistical consultant, [name]. The psychometrist and research associate will be blind to randomization status. All participants will continue to receive their usual

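### The H1a analysis set drops randomised Veterans who have only a baseline record, although the missing-data paragraph says early terminators are used; a minor conflict, settled by striking one phrase

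*Combined protocol and SAP*

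**What the plan says.** All references are to Section 9 (Design and Methods).

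- **Analytic Plan and Power Analyses, missing data:** nothing will be imputed because "our analytic method uses all existing data points, including all subjects with missing data or those who were terminated early in the study". Pattern-mixture models and a comparison of subjects with and without missing data are also planned.
- **H1a, statistical analyses:** "We will analyze data on all randomized subjects with a baseline assessment and at least one post-baseline evaluation".
- **H1a, model:** Time has four levels, weeks 0, 5, 10 and 15, and "A fully saturated treatment by time model will be utilized for inference". Baseline is therefore a modelled outcome with its own mean in each arm.
- **Procedure:** "participants will complete a baseline assessment and will then be randomly assigned". Every randomised Veteran should therefore have a baseline record.
- **Retention and the H1a power paragraph:** 98 are targeted and about 20% are expected to be lost, leaving 78 (39 per group). Neither place says how much of that loss falls before the first follow-up.

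**The concern.** The two statements cannot both be followed for a Veteran who is randomised and leaves before the first follow-up. Under the missing-data paragraph this Veteran is an early terminator with an existing data point and stays in. Under the H1a sentence the Veteran goes out, and no reason is given.

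In the planned model a baseline-only record is not empty. It informs the arm's baseline mean and, through the within-person correlation, the arm's later means. If loss is missing at random given baseline, this corrects the change contrast for who was lost. Dropping these Veterans conditions the comparison on an event after randomisation and gives up the correction. If the pattern-mixture analysis uses the same set, the earliest dropout pattern is missing from the sensitivity analysis as well. At stake is the comparison on both co-primary outcomes (the GDS composite and the UPSA-B) and on the WHODAS 2.0.

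**Working it through.** **1. The plan's own figures.** 98 × 0.8 = 78.4, so 78, or 39 per arm. With unit SD and the plan's correlation of .5, the variance of a baseline-to-week-15 change is 2(1 − .5) = 1. The standard error of the contrast is √(2/39) = .2265, and .72/.2265 = 3.179. The nominal alpha and the Bonferroni divisor are not stated. Assuming two-sided .05:

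- divided by 3: Φ(3.179 − 2.394) = .784
- divided by 2: Φ(3.179 − 2.241) = .826 (.812 by the noncentral t)

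The stated .80 is reproduced within about two points (.784 and, by t, .812).

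**2. Bias from the exclusion.** Let a fraction f of an arm leave before the first follow-up, with a baseline mean δ SD worse than the whole arm. The baseline mean of those kept then shifts by fδ/(1 − f). If loss depends on baseline only, their week-15 mean shifts by ρ times that. The bias in the change contrast has size (1 − ρ) × δ × [f₁/(1 − f₁) − f₀/(1 − f₀)]. With ρ = .5 from the plan, and f and δ assumed:

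| f₁ vs f₀ | δ | Bracket | Bias (SD) |
|---|---|---|---|
| 10% vs 5% | 0.5 | .1111 − .0526 = .0585 | .5 × .5 × .0585 = .015 |
| 15% vs 5% | 0.5 | .1765 − .0526 = .1238 | .5 × .5 × .1238 = .031 |
| 15% vs 5% | 0.8 | .1238 | .5 × .8 × .1238 = .050 |

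On a scale where higher is better, the bias runs against the arm that loses more of its worse-at-baseline Veterans. With equal loss of the same kind in both arms it is zero.

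**3. Precision when these Veterans are kept.** Take 49 per arm, 39 completers and compound symmetry with ρ = .5. If all 10 lost per arm have baseline only:

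- Excluded: variance per arm 2(1 − ρ)/39 = .02564; SE = √(2 × .02564) = .2265.
- Included: variance per arm (1 − ρ²)/39 + (1 − ρ)²/49 = .01923 + .00510 = .02433; SE = √(2 × .02433) = .2206.

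Generalised least squares gives the other cases, with the remaining dropouts seen at weeks 0 and 5 only. Power is for effect size .72 at alpha .05/3.

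| Baseline-only per arm | SE excluded | SE included | Fall | Power |
|---|---|---|---|---|
| 2 | .2199 | .2189 | 0.5% | .810 to .814 |
| 5 | .2221 | .2195 | 1.2% | .802 to .812 |
| 10 | .2265 | .2206 | 2.6% | .784 to .808 |

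Over correlations from .3 to .9, the ratio of included to excluded SE for this contrast runs from .964 to .999.

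**4. Where the correction works and where it fails.** Simulation with true effect 0, ρ = .5, 3,000 trials per case and 10 baseline-only Veterans per arm (all of the expected loss, so an extreme case):

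| Early loss | Bias excluded | Bias included |
|---|---|---|
| Random | .008 | .009 |
| Depends on baseline, one arm only | −.107 | .004 |
| Depends on baseline, opposite directions by arm | −.230 | −.003 |
| Depends on unobserved week-15 value, one arm only | .114 | .171 |

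**5. Common baseline mean.** If the two arms share one baseline mean, the week-15 effect is the post-baseline difference minus ρ times the baseline difference among those observed. The shift in step 2 then cancels whether or not baseline-only Veterans are kept. A large-sample simulation with 15% vs 5% baseline-dependent early loss gave a bias of about −.04 SD with exclusion and no constraint, and about 0 with either change alone.

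**The case against.** The missing-data paragraph describes the method in general, to explain why nothing is imputed, while the H1a sentence defines the analysis set. Veterans terminated early after one follow-up are kept under both. That stands: the conflict is confined to the baseline-only group.

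The effect is small and rests on assumed rates. A bias of .015 to .05 SD is 2% to 7% of the .72 design effect (.015/.72 and .05/.72) and less than a quarter of a standard error of about .22. The Retention text adds that attrition may fall below 20% because participants live on site. That also stands.

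A reader might infer three stronger things, and the documents support none of them:

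- **That the co-primary comparison is materially compromised.** The biases of −.107 and −.230 assume that every expected dropout leaves before the first follow-up and that loss follows baseline differently by arm. Nothing in the plan suggests either.
- **That inclusion cures early dropout.** It does so only if loss is missing at random given baseline. In the last case of step 4 the bias is larger with inclusion. Nor is the plan silent on dropout: it has pattern-mixture models, although it does not say whether they cover the baseline-only pattern.
- **That a common baseline mean belongs to the correction.** It would replace the stated saturated specification, and it removes the same bias by itself, so it is an alternative and not a necessary companion.

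**Conclusion.** The conflict holds and is minor. The H1a sentence discards an existing outcome record that the missing-data paragraph says is used. Within the planned saturated model, keeping these Veterans needs no new data, does not raise the standard error and leaves the target of 98 unchanged.

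The gain in validity is about .015 to .05 SD. It arises only if early loss depends on baseline and differs by arm, and its size assumes early loss of 10-15% vs 5% and leavers 0.5 to 0.8 SD worse at baseline. It could be near zero if few leave early or loss is similar across arms. Under loss that depends on unobserved outcomes there is no such gain, and the bias may grow.

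A reader might also infer that the edit removes every post-randomisation exclusion. It may not. The battery is given at all four time points, and the effort-test rule under Study Measures removes Veterans scoring below the cut-offs from the rest of the study, without limiting the rule to baseline. Who counts as baseline-only also depends on the assessment schedule. That is weeks 5, 10 and 15 in Section 7, Retention and H1a, but weeks 3, 12 and 15 under Procedure; these passages must be reconciled.

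**What to change.** In the H1a analysis sentence, end the definition after the baseline assessment by striking the requirement for a post-baseline evaluation, and add that subjects are analysed as randomised. State that the planned pattern-mixture analysis includes the baseline-only pattern as a pattern of its own. Because that pattern has no follow-up data, its later means need an explicit assumption, which should be written down in advance.

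The cost is one deleted phrase and one or two added sentences, with no new data, no change in sample size and no loss of precision. A common baseline mean may be considered separately. If adopted, the sentence on the fully saturated model would have to be rewritten to match.

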Electronic data will be stored on a secure research drive on our VA network, accessible only to VA research personnel associated with the proposed study. Electronic records will include a password-protected key linking subject numbers with subject names. Paper records will be coded by subject number only, and will not include participant names, with the exception of consent forms, which will be stored separately and will include names, but no subject numbers. All paper records will be kept in locked cabinets in a locked room. A custom-tailored database system will be developed for this project to ensure the highest possible data reliability. Data entry programs will include double data entry, item prompts, skip patterns, range checks, and logical validity routines. Consultation regarding data management and information security issues will be provided by [name], with whom [name] has worked for over 10 years.

Analytic Plan and Power Analyses

Data analyses will proceed in stages, with [name] serving as a statistical consultant during the award period. At first, descriptive statistics and exploratory graphing will be used to assess the normality of the data in terms of the presence of skewness and/or outliers. The continuous outcome data will be transformed if necessary by using an appropriate transformation such as the log transformation for skewed long tailed data. We will check to ensure that the randomization worked and there are no significant differences between the experimental and control groups on demographics, clinical characteristics, and/or baseline cognition/functional

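### H1a gives each arm its own week-0 mean although baseline precedes randomisation; using baseline better would gain precision at no data cost (about 24-25% of variance at the plan's correlation of .5, about 1-5% at .90-.95)

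*Combined protocol and SAP*

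**What the plan says.** The H1a paragraphs of Analytic Plan and Power Analyses (Section 9) give the independent variables as "Treatment group (CCT vs education control) and Time (0, 5, 10, 15 weeks"), so week 0 is part of the response. The mean structure is then fixed: "A fully saturated treatment by time model will be utilized for inference". The analysis set is stated as "We will analyze data on all randomized subjects with a baseline assessment and at least one post-baseline evaluation". The covariance structure is to be chosen by AIC, and the text describes random intercepts, random slopes and their correlation.

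The Procedure section gives the order of events: "participants will complete a baseline assessment and will then be randomly assigned to receive either CCT or the education control condition".

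The adjustment rules that can be read depend on imbalance. Design Considerations says that differences between the randomised groups, including level of cognitive impairment, will be allowed for if they arise. The Analytic Plan describes a check that there are "no significant differences between the experimental and control groups on demographics, clinical characteristics, and/or baseline cognition/functional". In the copy reviewed, the text breaks off there and resumes inside the description of the mixed model.

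The H1a power statement claims .80 power for an effect of .72 with 78 completers, a correlation of .5 between time points, one random effect and a Type I error correction. On multiplicity the plan says "Type I error will be controlled by a Bonferroni adjustment to the alpha per outcome domain for Hypotheses 1a and 1b". It states no divisor.

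**The concern.** A fully saturated model over two arms and four visits has eight free cell means, two of them at week 0. With complete data, the treatment contrast at a later visit is then the difference between arms in mean change from baseline. The chance difference between the arms at week 0 is subtracted in full, even though randomisation makes its expected value zero.

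Constraining the week-0 means to be equal, or conditioning on baseline, subtracts only the share that the correlation justifies. The plan itself favours the mixed model because it should have more power than a change score. With complete data, the stated mean structure gives back the change-score comparison.

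Precision is at stake, not validity. It matters because planned power is only .80, for a fairly large effect, at a single 40-bed site.

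**Working it through.** **Inputs.** 39 per arm after 20% attrition (Retention); d = .72 and rho = .5 (H1a power analysis); MCCB composite retest coefficient .90 (Study Measures) and .95 (Section 9.8). Assumed: unit SD at every visit, two-sided tests, and Bonferroni over two or three outcomes (alpha .025 or .0167). A correlation of .5 with one random effect is compound symmetry if that effect is a random intercept.

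**1. The plan's own figure.** 98 x .8 = 78.4, hence 78. At rho = .5 the SD of a change is sqrt(2(1 - .5)) = 1. The variance of the contrast is 2/39 = .0513, SE .226, and .72/.226 = 3.18. Noncentral t power (76 df) is .812 at alpha .025 and .766 at .0167. The normal approximation gives .826 and .784. The stated .80 is therefore reproduced approximately, without any use of a common baseline.

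**2. Effect of the change.** Per-arm variance:
- separate week-0 means: 2(1 - rho)
- common week-0 mean, or baseline as covariate: 1 - rho^2
- ratio (1 + rho)/2, so the cut is (1 - rho)/2

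Generalised least squares on the four-visit model confirms this. Estimating the baseline slope at N = 78 multiplies the constrained variance by about 1 + 1/74.

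| rho | separate | common | cut | cut at N = 78 |
|---|---|---|---|---|
| .5 | .0513 | .0385 | 25% | 24% |
| .7 | .0308 | .0262 | 15% | 14% |
| .90 | .0103 | .0097 | 5% | 3.7% |
| .95 | .0051 | .0050 | 2.5% | 1.2% |

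A simulation of ANCOVA against change score at N = 78 gives 24%, 4.3% and 1.4% at .5, .90 and .95.

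**3. Power at d = .72, rho = .5.** SE falls from .226 to .196. Power goes from .81 to .91 (alpha .025), or from .77 to .88-.89 (alpha .0167). At .90 or .95 it is above .99 under either model.

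**4. Dropout.** With 49 per arm, 20% lost evenly by week 15 and rho = .5, the variance goes from .0484 to .0375, a cut of 22.6%. Power at alpha .025 goes from .84 to .92. Other dropout timings give cuts of 21% to 25%.

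**5. Other contrasts and covariances.** The plan names no contrast. At rho = .5 under compound symmetry, the cut is 22.5% for a linear trend and 37.5% for the mean of the three changes. Under AR(1) the week-0 to week-15 correlation is .5^3 = .125, and the cut for that change is (1 - .125)/2 = 44%.

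With random slopes the visit variances differ. With week-0 variance 1, the cut is (1 - c)^2 / (1 + v - 2c), where c is the week-0/week-15 covariance and v the week-15 variance. Assume intercept variance .5 and residual variance .5, with slope variance taken over 15 weeks:

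| slope variance | intercept-slope correlation +.3 | 0 | -.3 |
|---|---|---|---|
| .25 | 12% | 20% | 29% |
| .5 | 8% | 17% | 28% |

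In the 12% case c = .606 and v = 1.462: .394^2 / 1.25 = .124. The week-0/week-15 correlation there is .50, so a correlation of .5 does not by itself guarantee a 25% cut.

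**The case against.** The strongest reply is that nothing is wrong. The saturated model is unbiased, and the stated power is met on the plan's own inputs without the change. That stands, and it is why this is an improvement and not a correction. A reader might infer that H1a is biased or underpowered; the documents support neither.

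Second, a baseline rule may sit in the text missing after the baseline check. That also stands: no omission can be charged to the plan, and the original must be read first. The adjustment in Design Considerations does not settle the matter, because it is conditional on observed imbalance and does not secure the gain in advance.

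Third, the benefit is uncertain. A reader might take 25% as the gain for the co-primaries. That figure needs equal visit variances, a single-visit contrast and rho = .5, whereas the plan allows random slopes and names no contrast. The only retest values given (.90 and .95) are for the MCCB composite and make the gain negligible. Those values, however, belong to neither the GDS composite nor the UPSA-B, and the plan itself chose .5.

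**Conclusion.** The point holds as a free improvement of minor to moderate size. As far as the plan can be read, H1a spends precision on separate week-0 means that randomisation makes unnecessary. For a single-visit change with equal visit variances and complete data, the variance cut is about 24-25% at the planning correlation and about 1-5% at MCCB-like stability. Under the assumed random-slope structures it is about 8% to 29%. The power gain of roughly ten points rests on rho = .5, d = .72 and an assumed Bonferroni divisor. The actual gain for either co-primary cannot be determined from the documents.

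A reader might extend the argument to H1b, using prior housing days as a covariate. The documents do not support a recommendation there. They give no correlation with the follow-up outcomes, and requiring homelessness or unstable housing at entry may restrict the covariate's range.

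**What to change.** Check the original text after the baseline comparison in Analytic Plan and Power Analyses. If it sets no baseline rule for H1a, keep the mixed model and prespecify one of these:

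- **Common week-0 mean.** Constrain the two arms to one mean at week 0 and include every randomised participant with a baseline. This drops the requirement for a post-baseline visit from the analysis set.
- **Baseline as covariate.** Model weeks 5, 10 and 15 as responses, with baseline and its interaction with visit as fixed terms. The stated analysis set is unchanged. With equal dropout by arm, leaving out baseline-only participants costs no precision (large-sample variance .0375 with or without them at rho = .5 and even dropout).

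State that the choice does not depend on the imbalance check. The cost is SAP wording and, for the covariate form, one to three degrees of freedom. No new data are needed, because the H1a outcomes are already collected at baseline.
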